10.4 Tissue Banking

Biologic specimens collected during the conduct of each clinical trial that are not used during the course of the study will be considered deliverables under the contract and thus the property of the NCI. At study completion, NCI reserves the option to either retain or relinquish ownership of the unused biologic specimens. If NCI retains ownership of specimens, the Contractor shall collect, verify, and transfer the requested biologic specimens from the site to a NCI-specified repository or laboratory at NCI's expense.

11. **REPORTING ADVERSE EVENTS**

DEFINITION: AE means any untoward medical occurrence associated with the use of a drug in humans, whether or not considered drug related. An AE can therefore be any unfavorable and unintended sign), symptom, or disease temporally associated with participation in a study, whether or not related to that participation. This includes all deaths that occur while a participant is on a study.

Please note that all abnormal clinical laboratory values that are determined to be of clinical significance based on a physician's assessment are to be reported as AEs. Those labs determined to be of no clinical significance or of unknown clinical significance (per the physician's assessment) should not be reported as AEs. Any lab value of unknown clinical significance should continue to be investigated/followed-up further for a final determination, if possible.

A list of AEs that have occurred or might occur can be found in §6.2 Reported Adverse Events and Potential Risks, as well as the Investigator Brochure or package insert.

11.1 Adverse Events

11.1.1 Reportable AEs

All AEs that occur after the informed consent is signed and baseline assessments are completed (including run-in) must be recorded on the AE CRF (paper and/or electronic) whether or not related to study agent.

11.1.2 AE Data Elements

The following data elements are required for AE reporting.

- AE verbatim term
- NCI Common Terminology Criteria for Adverse Events version 4.0 (CTCAE v4.0) AE term (MedDRA lowest level term)
- CTCAE (MedDRA) System Organ Class (SOC)

- Event onset date and event ended date
- Treatment assignment code (TAC) at time of AE onset
- Severity grade
- Attribution to study agent (relatedness)
- Whether or not the event was reported as a SAE
- Whether or not the participant dropped due to the event
- Outcome of the event

11.1.3 Severity of AEs

11.1.3.1 Identify the AE using the CTCAE version 4.0. The CTCAE provides descriptive terminology (MedDRA lowest level term) and a grading scale for each AE listed. A copy of the CTCAE can be found at http://ctep.cancer.gov/protocolDevelopment/electronic_applications/ctc.htm

AEs will be assessed according to the grade associated with the CTCAE term. AEs that do not have a corresponding CTCAE term will be assessed according to the general guidelines for grading used in the CTCAE v4.0 as stated below.

Grade	Severity	Description	
1	Mild	Mild; asymptomatic or mild symptoms; clinical or diagnostic	
		observations only; intervention not indicated.	
2	Moderate	Moderate; minimal, local or noninvasive intervention indicated;	
		limiting age-appropriate instrumental activities of daily living	
		(ADL)*.	
3	Severe	Severe or medically significant but not immediately life-threatening;	
		hospitalization or prolongation of hospitalization indicated;	
		disabling; limiting self-care ADL**.	
4	Life-threatening	Life-threatening consequences; urgent intervention indicated.	
5	Fatal	Death related to AE.	

CTCAE v4.0 general severity guidelines:

ADL

*Instrumental ADL refers to preparing meals, shopping for groceries or clothes, using the telephone, managing money, *etc*.

**Self-care ADL refers to bathing, dressing and undressing, feeding self, using the toilet, taking medications, and not bedridden.

11.1.4 Assessment of relationship of AE to treatment

The possibility that the AE is related to study agent will be classified as one of the following: not related, unlikely, possible, probable, definite.

11.1.5 Follow-up of AEs

All AEs, including lab abnormalities that in the opinion of the investigator are clinically significant, will be followed according to good medical practices and documented as such.

11.2 Serious Adverse Events

11.2.1 DEFINITION: Regulations at 21 CFR §312.32 (revised April 1, 2014) defines an SAE as any untoward medical occurrence that at any dose has one or more of the following outcomes:

- Death
- A life-threatening AE
- Inpatient hospitalization or prolongation of existing hospitalization
- A persistent or significant incapacity or substantial disruption of the ability to perform normal life functions
- A congenital anomaly or birth defect
- Important medical events that may not be immediately life-threatening or result in death or hospitalization should also be considered serious when, based upon appropriate medical judgment, they may jeopardize the patient and may require intervention to prevent one of the other outcomes.

11.2.2 Reporting SAEs to DCP

11.2.2.1 The Lead Organization and all Participating Organizations will report SAEs on the DCP SAE Report Form found at http://prevention.cancer.gov/clinical-trials/clinical-trials-management/protocol-information-office/pio-instructions-and-tools/2012-consortia.

11.2.2.2 Contact the DCP Medical Monitor by phone within 24 hours of knowledge of the event.

DCP Medical/Task Order Monitor [name] [name], FACS NCI/Division of Cancer Prevention [name] [name] 5[name] 20892 [contact] [contact] Email: [contact]

Include the following information when calling the Medical Monitor:

- Date and time of the SAE
- Date and time of the SAE report
- Name of reporter
- Call back phone number
- Affiliation/Institution conducting the study
- DCP protocol number
- Title of protocol
- Description of the SAE, including attribution to drug

11.2.2.3 The Lead Organization and all Participating Organizations will email written SAE reports to the following within 48 hours of learning of the event using the fillable PDF SAE Report Form.

- DCP's Regulatory Contractor CCS Associates, Inc. (CCSA; [contact]) at [contact]
- DCP Medical Monitor, [name] ([contact])
- Northwestern Cancer Prevention Consortium ([contact])

11.2.2.4 The DCP Medical Monitor and CCSA regulatory and safety staff will determine which SAEs require FDA submission as IND safety reports.

11.2.2.5 The Lead Organization and all Participating Organizations will comply with applicable regulatory requirements related to reporting SAEs to the CIRB/IEC.

11.2.3 Follow-up of SAE

Site staff should send follow-up reports as requested when additional information is available. Additional information should be entered on the DCP SAE Report Form in the appropriate format. Follow-up information should be sent to DCP as soon as available. All SAEs will be followed according to standard of care. SAEs possibly, probably, or definitely related to the study agent will be followed until resolved.

12. STUDY MONITORING

12.1 Data Management

Data will be managed by the study statistician, [name] according to standard operating procedures, which meet the guidelines of DCP Requirements for Data Management and which follow the Data Management Plan that Northwestern University has on file with the Division of Cancer Prevention, NCI. Source data verification will be performed by the Northwestern Cancer Prevention Consortium. The Consortia 2012 Data Management Plan, submitted as part of a contract agreement with the NCI (HHSN261201200035I), was approved.

Clinical data will be reported to Northwestern University through the Lurie Cancer Center Clinical Trials Management System (CTMS), which will be the database of record.

12.2 Case Report Forms

Participant data will be collected using protocol-specific case report forms (CRFs) developed from the standard set of DCP Chemoprevention CRF Templates and utilizing NCI-approved Common Data Elements (CDEs). The approved CRFs will be used by Northwestern University to create the electronic CRFs (e-CRFs) screens in the CTMS-RDC application. Site staff will enter data into the e-CRFs for transmission to DCP according to DCP standards and procedures.

All specimen results that are batch analyzed will be collected and stored on excel spreadsheets. The excel spreadsheets will constitute the database of record.

12.3 Source Documents

All source documents will be collected and stored by the research staff at the site of accrual. Any data recorded directly in CTMS that constitute no prior written or electronic record of data, will be specifically identified as source data. Questionnaires completed in person may be completed on the paper and entered into CTMS.

12.4 Data and Safety Monitoring Plan

A comprehensive Data Safety and Monitoring Plan has been submitted by Northwestern University, approved by the DCP, and is on file there. Any future changes will be forwarded for review.

This trial is subject to review by the Lurie Cancer Center Data Monitoring Committee (DMC). Semi-

Annual reports, SAEs, and protocol deviations will be reviewed by the DMC at bi-weekly meetings. This trial is also subject to possible annual audits by the Lurie Cancer Center Clinical Trials Audit Committee (CTAC).

12.5 Sponsor or FDA Monitoring

The NCI, DCP (or their designee), pharmaceutical collaborator (or their designee), or FDA may monitor/audit various aspects of the study. These monitors will be given access to facilities, databases, supplies, and records to review and verify data pertinent to the study.

12.6 Record Retention

Clinical records for all participants, including CRFs, all source documentation (containing evidence to study eligibility, history and physical findings, laboratory data, results of consultations, etc.), as well as IRB records and other regulatory documentation will be retained by the Investigator in a secure storage facility in compliance with Health Insurance Portability and Accountability Act (HIPAA), Office of Human Research Protections (OHRP), Food and Drug Administration (FDA) regulations and guidances, and NCI/DCP requirements, unless the standard at the site is more stringent. The records for all studies performed under an IND will be maintained, at a minimum, for two years after the approval of a New Drug Application (NDA). For NCI/DCP, records will be retained for at least three years after the completion of the research. NCI will be notified prior to the planned destruction of any materials. The records should be accessible for inspection and copying by authorized persons of the Food and Drug Administration. If the study is done outside of the United States, applicable regulatory requirements for the specific country participating in the study also apply.

12.7 Cooperative Research and Development Agreement (CRADA)/Clinical Trials Agreement (CTA)

Not applicable.

13. STATISTICAL CONSIDERATIONS

13.1 Study Design/Description

This is a randomized double-blinded, placebo-controlled Phase II trial of statin to evaluate the impact of statin treatment on disease progression in 80 patients with liver cirrhosis who have a current Model for End-Stage Liver Disease (MELD) ≤ 20 and no evidence of hepatocellular carcinoma (HCC). The primary objective of this study will be to demonstrate that statins will improve liver function in high-risk patients. The primary outcome is change from baseline (Study Visit 1) at 6 months in AFP-L3%. Secondary outcomes will include additional measures of liver function (serum AFP, IL-6 and DCA levels, liver stiffness, FIB-4 score, and MELD score).

13.2 Randomization/Stratification

Patients will be randomized by the study statistician at Northwestern University. Randomization will be carried out among consented patients meeting the Screen 1 eligibility criteria at each site (CSMC, NWU, GU, and UPR) with a 1:1 ratio for simvastatin and placebo assignment.

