6.8 Registration/Randomization

- 1. A study coordinator must upload into the Northwestern Clinical Trials Management System, a signed and complete informed consent along with HIPAA authorization and a completed eligibility form for each participant identified as eligible to be entered into the study.
- 2. All participants must be registered in the Northwestern University Robert H. Lurie Comprehensive Cancer Center Clinical Trials Management System (CTMS). Participants must not start protocol treatment prior to registration in the Lurie Cancer Center CTMS.
- 3. After registration in the CTMS, participants will be assigned a participant identification number and a randomization number when applicable.
- 4. An NCPC Quality Assurance Monitor will submit the following into the REDCap Randomization Information Form: (1) Study Number, (2) Site, (3) Pharmacist Email(s), (4) Participant ID, (5) Participant Initials, and (6) Randomization Date.
- An Automatic Treatment Assignment Notification email will be sent to the research pharmacist(s) containing: (1) Study Number, (2) Site, (3) Participant ID, (4) Participant Initials, (5) Randomization Date, and (6) Treatment Assignment.
- 6. The clinical research coordinator(s) will receive a Confirmation of Registration containing the PID via email.
- 7. The following people will have a copy of the un-blinded randomization log: the study statistician at NU, the Quality Assurance Team at NU, and the Investigational Pharmacists at each site. The following people will have access to the REDCap study project containing randomization information: the study statistician at NU and the Quality Assurance Team at NU. The study statistician will set up randomization blocks.

When possible, the study coordinator will notify an NCPC Quality Assurance Monitor and/or send an email to [contact] prior to registering a participant. Prior notification is required for participant randomizations outside the normal business hours of Monday-Friday 9:00am-5:00pm CT.

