13.4 Primary Objective, Endpoint(s), Analysis Plan

The primary outcome for this study is change from baseline to 6 months in AFP-L3%. Power calculations are presented in Table 2. In the treatment group, we expect change of 2.8 over 6 months, and in the

	Table 2. Numeric Results for Mann-Whitney Test									
a change of 0, with	Power	N1	N2	Ratio	Alpha	Beta	Mean1	Mean2	S1	S2
standard deviation=5.3 in	0.81	36	36	1	0.1	0.19	2.8	0	5.3	5.3
both groups (or smaller). Null Hypothesis: Mean1=Mean2. Alternative Hypothesis: Mean1>Mean2.										
For a Phase II study we The standard deviations were assumed to be unknown and unequal.										

have an acceptable alpha of 10%. For the primary endpoint, AFP-L3%, we will consider changes D(T) and D(P) for D=After-Before, for simvastatin (T) and placebo (P) groups, respectively. We will use a nonparametric two-sample Wilcoxon-Mann-Whitney test to address the hypothesis H0: mean [D(T)] =mean [D(P)] versus H1: means[D(T)] > mean [D(P)] and report a defined one-sided p-value. If p<0.1 we will consider this to be evidence of an effect of simvastatin on AFP-L3%. If p>0.1 we will report the actual means and the corresponding confidence intervals observed and declare the trial had failed. If we observe: mean[(D(P)] > mean[D(T)] which would be unexpected, we will declare the trial failed and discuss possible explanations for the observed situation, which would suggest possibly adverse effect of the treatment. We are expecting less than 1 participant to progress to HCC in either the placebo or treatment arms during the course of the study [8].

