13.5 Secondary and Exploratory Objectives, Endpoints, Analysis Plans

For the continuous secondary endpoints (serum AFP, IL-6, serum DCA, liver stiffness, FIB-4 score, and MELD score) and exploratory endpoints, we will consider D(T) and D(P) as well as percent change relative to baseline, namely, D(T)/B(T) and D(P)/B(P). Biomarker levels at baseline and 6 months, as well as changes from baseline to 6 months, will be summarized using descriptive statistics and graphical methods. ANCOVA models with post-treatment value as the outcome, and treatment group and baseline value as predictors will be used to examine treatment differences. In these models, the estimated coefficient for treatment is the difference between the mean change scores of each arm [116]. Model fit will be assessed using standard model diagnostics including residual plots, influence statistics, and model assumptions such as normality and equivariance, will be verified. Potential outliers will be identified and reasons for extreme values will be investigated. Biomarker values may be transformed, e.g. logarithmically, to satisfy the normality assumption. Interaction between treatment group and baseline will be tested. Additional models that further adjust for other baseline characteristics, including routine clinical tests that have been shown to be strongly predictive of HCC diagnosis in prospective cohorts of cirrhosis such as higher alkaline phosphatase [6], lower platelets [6, 71, 73, 117], lower albumin [73, 118], and lower prothrombin activity [119]. We will also consider clinical variables representing important HCC risk factors captured through the epidemiological questionnaire (Appendix F), including body mass index, current alcohol use, and current dietary fat, carbohydrate, fiber, coffee, and antioxidants [99-112]. The change in variable criterion will be used to identify confounders for our final models. Model selection will be performed using the purposeful model selection approach [120], resulting in a parsimonious model that includes adequate control for confounding. Adjusted treatment effects will be

reported.

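### Patients are randomised at each of four sites, most naturally in blocks within site, but neither the primary Wilcoxon test nor the secondary ANCOVA uses site: a minor conservatism that the ANCOVA can shed at no measurable cost.

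*Combined protocol and SAP*

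**What the plan says.** Section 13.2, under a heading that names both randomisation and stratification, states: "Randomization will be carried out among consented patients meeting the Screen 1 eligibility criteria at each site", naming CSMC, NWU, GU and UPR, at 1:1. Section 6.8 makes site a field of the randomisation form and adds: "The study statistician will set up randomization blocks". Neither section says that the blocks lie within site, gives a block size, or calls the scheme stratified.

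The primary analysis (13.4) is a "nonparametric two-sample Wilcoxon-Mann-Whitney test to address the hypothesis" of equal change in the two arms, at a 10% level with a one-sided p-value. No stratum is named.

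In the secondary and exploratory models (13.5), "treatment group and baseline value as predictors will be used to examine treatment differences". The further adjusted models list laboratory tests, body mass index, alcohol and diet, and Section 4.4 says Child-Pugh class will be considered. Site is named in no analysis, and no reason is given for leaving it out.

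**The concern.** Blocking within site makes the arms nearly equal in size at each site, so differences between sites largely drop out of the treatment contrast. An analysis that ignores site still counts that variation as error. The p-values are then too large and the intervals too wide. With planned power of 0.81, and 13.4 declaring the trial failed if p exceeds 0.1, even a few points of power are worth having if they cost nothing. What is at stake is precision. The validity of a positive result is not in question.

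**Working it through.** **Inputs from the plan.** One-sided alpha 0.10, difference 2.8, SD 5.3, 36 analysed per arm, stated power 0.81 (13.4, Table 2); 72 analysed of 80 randomised (13.3). Site pools (4.4, registered plus new): CSMC 187 + 110 = 297, NWU 77 + 140 = 217, GU 269 + 224 = 493, UPR 15 + 55 = 70; total 1077. In proportion, 72 patients split about 20/14/33/5 (for UPR, 72 × 70/1077 = 4.7).

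**Assumptions, not in the plan.** Site share of outcome variance ρ from 0 to 30%; blocks of 4 within site; normal data; for the ANCOVA, a baseline slope of 0.6.

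**Step 1: the plan's own figure.** With Wilcoxon efficiency 3/π, the effective n per arm is 36 × 3/π = 34.4. Power = Φ(2.8 / (5.3 × √(2/34.4)) − 1.2816) = 0.818. Simulating the Wilcoxon test gives 0.812–0.814. The stated 0.81 reproduces.

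**Step 2: why ignoring site is conservative.** The unadjusted SE of the mean difference is 5.3 × √(2/36) = 1.25. With exact balance within site and total SD held at 5.3, the true SE is 1.25 × √(1 − ρ), and the actual level is about 1 − Φ(1.2816/√(1 − ρ)). At ρ = 20%, this gives a true SE of 1.12 and a level of 0.076. Incomplete blocks soften this slightly, so simulation was used for the figures below.

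**Step 3: primary test.** Site effects were generated in two ways: fixed, with the realised share held exactly at ρ (40,000 trials per setting), and random, with variance share ρ (20,000 trials). Random effects give milder results. With four sites of these sizes, the mean realised between-site variance is only 1 − (20² + 14² + 33² + 5²)/72² = 1 − 1710/5184 = 0.67 of nominal. Ranges below span the two; the SE column is for the fixed case.

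| ρ | Reported / true SE | Level of planned Wilcoxon | Power, planned | Power, van Elteren | Power, site-aligned |
|---|---|---|---|---|---|
| 0% | 1.25 / 1.25 | 0.10 | 0.81 | 0.80 | 0.81 |
| 5% | 1.25 / 1.22 | about 0.095 | 0.82 | 0.82 | 0.83 |
| 10% | 1.25 / 1.19 | 0.09–0.095 | 0.82–0.83 | 0.83 | 0.84 |
| 20% | 1.25 / 1.125 | 0.08–0.087 | 0.84–0.85 | 0.86–0.865 | 0.87–0.875 |
| 30% | 1.25 / 1.06 | 0.07–0.08 | 0.85–0.87 | 0.90 | 0.905 |

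The reported SE is too large by about 0 / 2 / 5 / 11 / 18%. Both site-based tests hold a level of about 0.10 throughout. Van Elteren loses about 1 point at ρ of 0–2%, breaks even near 10% and gains 1 to 3 points at 20%. At 30%, the far end of the range, it gains about 3 points with random effects and nearly 5 with fixed.

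**Step 4: ANCOVA (random site effects, split 20/14/33/5).**

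| ρ | Level without / with site | Power without / with site |
|---|---|---|
| 0% | 0.102 / 0.102 | 0.826 / 0.825 |
| 5% | 0.099 / 0.103 | 0.835 / 0.839 |
| 10% | 0.095 / 0.102 | 0.840 / 0.849 |
| 20% | 0.084 / 0.100 | 0.859 / 0.882 |
| 30% | 0.077 / 0.099 | 0.880 / 0.913 |

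The gain is about 0 / 0.5 / 1 / 2 / 3 points. With the share held exactly, it reaches about 5 points at 30%. Site uses three degrees of freedom (residual 69 becomes 66), and at ρ = 0 the loss is within simulation error.

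**The case against.** Most of the case against concerns size, and much of it stands.

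- **A reader might take Section 4.4 as proof that sites differ**, since it expects 94, 79, 78 and 69% of listed patients to have MELD of 20 or less. Those figures describe waitlists before the MELD >20 exclusion (4.2.9). They show who is screened out, not how enrolled patients differ.
- **For AFP-L3%, the site share may be small.** Stable site differences in level cancel in the change score, and the assay is run in one batch at one laboratory (7.6, 9.1). No document points to site differences in six-month change.
- **Normal data do not fit this endpoint.** Section 2.3 gives a median and lower quartile of 0.5% in cirrhosis without HCC, equal to the assay limit, so many changes will tie near zero. In an illustrative floored log-normal model with site differences in level only (parameters assumed), the planned test ran at 0.100, with power 0.775 against 0.767 for van Elteren. There was no conservatism to recover.
- **Blocking within site is inferred.** Under simple randomisation that ignores site, the SE would not be biased.
- **Power never falls below plan.** In the normal-data settings of Step 3, the planned test keeps at least about 0.81. A reader might infer an invalid or underpowered primary analysis; neither follows.

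These points do not reach the ANCOVA. FIB-4 and MELD inputs come from site or external clinical laboratories (10.1), and FibroScan is performed at study visits. A baseline slope below 1 also removes a stable site offset only in part. Site effects are plausible there, and adjusting for them costs nothing measurable.

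**Conclusion.** The point holds as a minor one. Site is absent from both analyses of a trial most naturally read as block-randomised within site. If that reading is right and sites differ in mean outcome, the analyses are mildly conservative, and the type I error stays at or below nominal. The ANCOVA change is a free improvement. For the primary test, the expected gain is small and can be slightly negative with van Elteren, so it is optional. The site share, block size, site split and normal errors are all assumptions; the direction rests only on within-site blocking and some site difference in the outcome analysed.

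**What to change.** 1. **Sections 13.2 and 6.8:** state whether the blocks are within site, and record the block structure in a document kept from site staff.
2. **Section 13.5:** add site as a fixed term to every ANCOVA, including the further adjusted models, and keep it outside covariate selection. The cost is one sentence, one model term and three degrees of freedom.
3. **Section 13.4, optional:** use a site-aligned rank test, which lost nothing in the normal-data simulation when sites did not differ, or van Elteren, which lost about 1 point. Because many changes may tie, check the choice on skewed, floored data first.
4. **Small sites:** prespecify a rule for pooling a site with very few analysed patients or none in one arm, since UPR may contribute about 5.

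All of this should be fixed before unblinded outcome data are analysed.
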